5.8 Receiving, Storage, Dispensing and Return

5.8.1 Receipt of Drug Supplies

Mirena will be shipped by Bayer Pharmaceuticals to the Mayo Clinic Outpatient Research Pharmacy and dispensed from there. Tranexamic acid tablets will be supplied by the Mayo Clinic Outpatient Research Pharmacy.

Upon receipt of the of the study treatment supplies, an inventory must be performed and a drug receipt log filled out by the person accepting the shipment. It is important that the designated study staff counts and verifies that the shipment contains all the items noted in the shipping invoice. Any discrepancies, damaged or unusable study drug in a given shipment (active drug or comparator) will be documented in the study files. The sponsor-investigator must be notified immediately of any discrepancies, damaged or unusable products that are received.

5.8.2 Storage

Mirena (levonorgestrel-releasing intrauterine system)

Store at 25°C (77°F); with excursions permitted between 15–30°C (59–86°F) [see USP Controlled Room Temperature].

Tranexamic acid tablets

Store at room temperature 25° C (77° F); excursions permitted to 15-30° C (59-86° F). [See USP Controlled Room Temperature].

All study drugs will be dispensed from the Mayo Clinic Outpatient Research Pharmacy. The drugs will be stored in a secure location according to product storage guidelines.

5.8.3 Dispensing of Study Drug

Investigational product will be dispensed by Mayo Clinic Outpatient Research Pharmacy per standard methods.

Regular study drug reconciliation will be performed to document drug assigned, drug dispensed, drug returns, and drug remaining. This reconciliation will be logged on the drug reconciliation form, and signed and dated by the study team.

5.8.4 Return or Destruction of Study Drug

Tranexamic acid and Mirena (levonorgestrel-releasing intrauterine system)

At the completion of the study, there will be a final reconciliation of drug shipped, drug dispensed, drug returns, and drug remaining. This reconciliation will be logged on the drug reconciliation form, signed and dated. Any discrepancies noted will be documented and

investigated, prior to return or destruction of unused study drug. Drug destroyed on site will be documented in the study files.

6 Study Procedures

Table 1.	Enrollment	4-6 Week Visit (Levonorgestrel IUS visit)	3 mo	6 mo	9 mo ⁶
Study visit	X				X
Informed Consent	X				
Phone follow-up			X	X	
Demographic and medical questionnaire	X				
Rand Short Form-36	X		X	X	X
UFS-QOL	X		X	X	X
MMAS	X		X	X	X
PBLAC (for each menses during the 9 mo.)	X		X	X	X
Visual analogue scale (VAS) for Pain	X		X	X	X
Adverse events			X	X	X
Request for relevant medical records	X				X
Medical records review	X				X
Ultrasound imaging	X ¹				X
Screening examination (uterine sounding length, estimation of uterine size by bimanual examination, and review of imaging)	X				
Phlebotomy– CBC ² , ferritin ²	X				X
Phlebotomy– creatinine ³	X				
Study remuneration					X
Pregnancy test (urine) – if needed	X				
History and Physical	X				X
Ultrasound to confirm placement of levonorgestrel IUS	X ⁴				
Levonorgestrel IUS visit		X ⁵			

¹Will only be performed if the ultrasound is not done for clinical purposes or no pelvic imaging (Saline infused sonogram, ultrasound, MRI) has been performed for more than 1 year before enrollment

²Will be performed if CBC, ferritin were not done for clinical purposes in the 3 months before enrollment

³Patients without renal disease can have creatinine pending at the time of enrollment, but will be withdrawn if result is ≥ 1.4 . Creatinine will not be drawn for the observation cohort unless clinically indicated at the time of initiation of treatment.

⁴If enrolled in the LNG-IUS arm of the randomized cohort.

⁵Will be performed 4-6 weeks after placement of LNG-IUS for confirmation of IUS location

⁶Or at withdrawal from or termination of the study

6.1 Visit 1/ Enrollment

The screening examination will include any screening elements not already completed during clinical evaluation (uterine sounding length, estimation of uterine size by bimanual examination, and review of imaging) or completed more than 6 months prior to enrollment. At this visit, subjects

will complete the questionnaires listed in the table and have laboratory testing completed. Pregnancy test will be performed for those at risk for pregnancy. If patients are current users of hormonal treatments for uterine bleeding and wish to enroll, they can be screened for the study. If eligible for the randomized cohort, they will need to complete a 1 month washout period with no hormone use and with natural resumption of their menses before they can be randomized to treatment. If they are current users of hormonal treatments and are switched to TA or LNG-IUS (with discontinuation of other hormonal treatments), they are eligible for the observation arm without washout. If enrolled in the LNG-IUS arm, ultrasound will be performed following placement to ensure the correct position of the LNG-IUS. If the LNG-IUS is not in the optimal position, it will be removed and a new device inserted immediately.

6.2 Week 4-6 Visit (For women enrolled in the LNG-IUS arm)

For women enrolled in the LNG-IUS arm, a visit will be scheduled at 4-6 weeks after placement to check for IUS strings visible at the cervix. This will serve as confirmation of position of IUS. If strings are not visible, clinical evaluation will be performed including pelvic ultrasound and/or x-ray to confirm location of IUS or expulsion.

6.3 Visit 2 / Month 3

At month 3, subjects will complete questionnaires listed in the table and receive a phone call to screen for adverse events. LNG-IUS that are expelled may be replaced one time if patient desires to continue device and the expulsion occurred within the prior 7 days. The expulsion occurred within one week and. Patient outcome would be recorded as expulsion.

6.4 Visit 3 / Month 6

At month 6, subjects will complete questionnaires listed in the table and receive a phone call to screen for adverse events.

6.5 Visit 4 / Month 9

At month 9, subjects will return for a study visit and examination. Ultrasound will be performed for size of fibroids. Laboratory testing will be completed. Subjects will complete questionnaires listed in the table and screen for adverse events and finalize study participation. Participants assigned to the LNG-IUS arm will be carefully assessed to determine if there are any contraindications to continuing therapy. Those with cavity-distorting fibroids (Type I) will be counseled regarding removal of the LNG-IUS.

7 Statistical Plan

7.1 Sample Size Determination

Aim 1. The primary outcome variable will be the difference in MMAS score at 6 months between the treatment arms. Based on the ECCLIPSE trial, the observed effect size at 6 months for the MMAS total score was 0.58 standard deviations (8). In order for the proposed trial to

have 90% power to detect such a difference, we would need 64 patients per treatment arm. To allow for up to 20% loss to follow-up or incomplete data without the potential to carry-forward an MMAS score from an earlier assessment, we will enroll 80 patients per treatment arm. From our preliminary study of a large insurance-claims database, we found a 40% difference (62% vs. 22%) in continued use of the index medication at 6 months. Based on the sample size of 80 women per arm, we will have over 90% power to detect such a difference if it exists in the data from the proposed trial. These calculations are based on a two-sample t-test and chi-square test, respectively, assuming a type I error of 0.05 and a two-sided alternative hypothesis.

Aim 2. As described in Aim 1, we plan to enroll 80 patients in each treatment arm. Among these 160 patients, we anticipate that at least 80 patients will have intentionally discontinued treatment by the end of the study. Table 3 below summarizes the detectable hazard ratios for different factor scenarios with varying prevalence. Assuming that 50% of the study participants will have a BMI > 30 kg/m², this aim will have 80% power to detect an association between obesity and intentional discontinuation.

Table 2. Detectable hazard ratios with 80% power based on a two-sided logrank test with a type I error of 0.05	
Prevalence of factor	Among the 160 patients in both arms (assume 80 intentionally discontinue)
20%	2.19
30%	1.98
40%	1.90
50%	1.88

7.2 Statistical Methods

Descriptive Statistics

Standard descriptive statistics will be generated for measurements at baseline, 3, 6, and 9 months, including mean, median, standard deviation (SD), and interquartile range (IQR) for continuous variables and counts and percentages for categorical variables.

Handling of Missing Data

Last value carry forward (LVCF) methods will be investigated to accommodate drop-outs.

Primary Hypothesis: A user-independent medical therapy (LNG-IUS) will result in better patient reported outcomes and longer use compared to self-administered medication (TXA)

Statistical analysis: The distribution of each of the continuously scaled outcome measures (MMAS total score, PBLAC score, ferritin level, hemoglobin level, UFS-QOL scores, and Rand

SF-36 composite scores) will be graphically evaluated and logarithmic transformations will be applied if the distributions are skewed in order to obtain more normally distributed distributions. At 3, 6, and 9 months separately, each of the continuously scaled outcomes will be compared between treatment arms based on fitting separate linear regression models. In addition, separate analysis of covariance (ANOCOVA) models will be fit to compare the measures between the two treatment arms after adjusting for baseline levels. The cumulative incidence (CI) function will be used to estimate the cumulative proportion of patients by time t who have intentionally discontinued treatment due to the desire or need to stop or switch treatment, after accounting for the competing risk of LNG-IUS expulsion and censoring all other participants at their date of last follow-up or end of study. Likewise we will also estimate the CI of expulsion among the LNG-IUS treatment arm. The CI estimates for intentional discontinuation over the entire 9 months of follow-up will be compared between treatment arms using the methods developed by Gray (34). All analyses will be performed based on the intention to treat principle and calculated p-values will be based on two-sided hypothesis tests. P-values less than 0.05 will be considered statistically significant. Statistical analyses will be performed using the SAS version 9.4 software package and packages in R (Version 3.1.1).

Secondary Hypothesis 1: Large fibroid size will limit the effectiveness of LNG-IUS compared with TXA; elevated BMI predicts higher success with LNG-IUS over TXA.

Statistical analysis: The primary event of interest is unsuccessful medical therapy, defined as the intentional discontinuation of treatment due to the desire or need to stop or switch treatment. However, the analysis is complicated by the fact that women in the LNG-IUS have a competing cause of failure, namely expulsion. Since the covariates associated with intentional discontinuation of treatment may be different from those associated with expulsion it will be important to analyze expulsion as a competing risk (35). We will first explore the associations between the covariates of interest and the competing risks by fitting separate Fine-Gray models for each type of failure using the `finegray` function in the `survival` package in R. We will also utilize the `mstate` package in R to further explore these associations. We will also explore whether the factors associated with intentional discontinuation differ between the two treatment arms.

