Our preliminary data from a large insurance-claims database show that women with fibroids were more likely to continue use of LNG-IUS (62% at 6 months) than TXA (22% at 6 months) for the treatment of HMB; however, we were unable to ascertain reasons for discontinuation in either group (16). Accurately predicting which women with fibroids are optimal candidates for medical therapy is a key unanswered question of the Agency for Healthcare Research and Quality (AHRQ) evidence-based review and would have substantial impact on the clinical care for women with fibroids (17).

Thus, we propose a **randomized controlled trial (RCT)** to assess the **comparative effectiveness** of LNG-IUS to TXA for the **treatment of HMB in women with clinically-significant fibroids**. We will measure patient-reported outcomes recognized to be important to women with HMB and study the clinical factors (e.g. body mass index, age) and fibroid factors (e.g. size, location) that predict successful medical therapy.

After greater than 1 year of enrollment and randomization, we have found that we have a higher rate of drop outs in the TXA arm than expected. Nearly all participants in the TXA arm have dropped out (n=4) before 6 months participation due to various side effects. Clinically, we use this medication and do not receive the same reported side effects. Thus, we would like to evaluate the use of TXA in a population that has self-selected the use of the medication. **We will add an observational arm to the study for women who otherwise meet study criteria and select either TXA or LNG-IUS, but decline randomization.**

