3.2 Primary Study Endpoints

The primary endpoints are the difference in self-reported MMAS scores at 6 months between LNG-IUS and TXA treatment and the duration of use of TXA versus LNG-IUS

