4.4 Early Withdrawal of Subjects

4.4.1 When and How to Withdraw Subjects

Participants may be withdrawn from the study at any time prior to completion of the study for the following reasons:

- Safety issues including allergic or adverse reaction to either medication
- If the participant develops clinically significant anemia from on-going HMB, she will be offered different treatment options
- Displacement of LNG-IUS will require removal and participant may opt to withdraw from study or have a new device placed
- Participant decision to withdraw from study (withdrawal of consent)
- Unable to comply with the study protocol

There are no adverse effects from stopping either treatment suddenly. We will encourage the participant to complete the study end measures (clinical laboratories, ultrasound, exam) to provide useful information to provide their primary care or gynecological provider on the management of their HMB. This data will be useful to understand the treatment effect on the fibroids, bleeding, and well-being of the participants. If withdrawn from the study and not agreeable to the additional measures, we will use only data collected to that point. We will plan our recruitment to account for 20% attrition from the study so that individual participants will not require replacement.

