4.4.2 Data Collection and Follow-up for Withdrawn Subjects

We will use the data obtained up until the person withdraws from the study, but will attempt to obtain permission for follow-up at 9 months for the subjects who have withdrawn. This endpoint will include whether the participant is still using either of the treatments, has any adverse events from treatment, had other procedures for HMB, and if there was expulsion of intrauterine device.

[figure not shown]
5 Study Drug

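### No month-6 MMAS is scheduled for women withdrawn from the study and no primary missing-data method is fixed, so early TXA drop-out leaves a primary comparison open to bias

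*Combined protocol and SAP*

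**What the plan says.** Section 3.2 sets the endpoint: "The primary endpoints are the difference in self-reported MMAS scores at 6 months between LNG-IUS and TXA treatment", alongside duration of use. Section 7.3 analyses every randomised woman by intention to treat. Section 6.4 and Table 1 schedule the MMAS at months 3, 6 and 9, so a woman who stops treatment but stays in the study still has a month-6 score due.

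Withdrawal from the study is treated differently. The reasons in section 4.4.1 for which a woman may be withdrawn include "Safety issues including allergic or adverse reaction to either medication". She is encouraged to complete end-of-study laboratory tests, ultrasound and examination; the MMAS is not listed there. Then: "If withdrawn from the study and not agreeable to the additional measures, we will use only data collected to that point". Section 4.4.2 seeks permission for one contact at 9 months, and "This endpoint will include whether the participant is still using either of the treatments, has any adverse events from treatment", with other procedures and device expulsion also named. MMAS is not named, though the list is not said to be complete. Footnote 6 of Table 1 lets the 9-month column, which includes MMAS, be completed at withdrawal.

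On missing scores, section 7.2 says "Last value carry forward (LVCF) methods will be investigated to accommodate drop-outs", and the study summary says the same. No other method and no sensitivity analysis is given. On expected loss, section 4.4.1 says "We will plan our recruitment to account for 20% attrition from the study". Section 1.1 reports what has happened: "we have found that we have a higher rate of drop outs in the TXA arm than expected", and "Nearly all participants in the TXA arm have dropped out (n=4) before 6 months participation due to various side effects". The stated response is an observational arm.

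**The concern.** An intention-to-treat comparison at month 6 needs a month-6 score, or a defensible stand-in, for each randomised woman. For withdrawn women the plan provides neither. A score taken at withdrawal describes the woman when she left. If she then stops or switches treatment, her month-6 score may be better or worse than the one carried forward. Reasons for discontinuation recorded so far (section 1.3) include lack of effect, pelvic pain and dysmenorrhoea, which are plausibly related to what the MMAS measures.

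If loss is heavier in one arm, the errors in carried scores need not cancel. Dropping the missing scores instead is also open to bias and costs power. Because section 7.2 only says that LVCF will be investigated, the choice between the two could be made after the data are seen. The observational arm cannot supply scores missing from the randomised comparison, and month-6 scores not collected at the time cannot be recovered later.

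**Working it through.** **1. The plan's own figure.** Section 7.1: effect 0.58 SD, two-sided 5%, 90% power, two-sample t-test. The noncentral t gives 63.4, so 64 per arm (power 90.2%); 64 / 0.8 = 80 enrolled per arm. The sample size reproduces, and no stated figure is wrong. But the 20% covers only women with no earlier score to carry forward, so it does not limit the number of carried scores.

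**2. Bias under LVCF.** Let qT and qL be the shares of the TXA and LNG-IUS arms whose score is carried forward, and gT and gL the mean true month-6 score minus the carried score, in SD, coded so that higher is better. For LNG-IUS minus TXA:

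bias = qT × gT − qL × gL

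The documents give none of the four quantities.

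**3. Assumed loss.** Section 7.1 cites claims data with continued use at 6 months of 62% (LNG-IUS) and 22% (TXA), so 38% and 78% stopped. That is stopping of treatment, not loss of MMAS; here it supplies only a ratio between arms. Splitting 20% overall attrition (arm shares summing to 0.40) in that ratio:

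- TXA: 0.40 × 78/116 = 26.9%
- LNG-IUS: 0.40 × 38/116 = 13.1%

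**4. Results at the planned attrition.** With a common gap g, bias = (0.269 − 0.131) × g.

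| Gap (SD) | Bias (SD) | Share of 0.58 SD | Type I error |
|---|---|---|---|
| 0.25 | 0.03 | 6% | 5–6% |
| 0.50 | 0.07 | 12% | 7–8% |

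Type I error comes from simulated trials with 80 per arm, no true difference, and assumed correlation of 0.3 or 0.5 between scores, for both unadjusted regression and ANCOVA. A noncentral-t check agrees: the standard error is √(2/80) = 0.158, and a shift of 0.069 rejects 7.2% of the time unadjusted and 7.9% with ANCOVA at correlation 0.5. Negative gaps reverse the sign.

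**5. Sensitivity to the assumptions.**

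- Half of the claims-data stoppers lost (39% vs 19%), common gap 0.5: 0.20 × 0.5 = 0.10 SD; type I error 9–11%.
- 20% attrition, gT 0.5 and gL 0: 0.269 × 0.5 = 0.13 SD; type I error about 12–17%.
- 20% attrition, gT 0.25 and gL 0.5: 0.067 − 0.066, about 0.
- 20% attrition, gT 0.2 and gL 0.6: 0.054 − 0.079 = −0.02 SD; the sign reverses.

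**6. Dropping missing scores instead.** At 27% vs 13% loss, 58 and 70 women remain and power at 0.58 SD is 90%. At 39% vs 19%, 49 and 65 remain and power is 86%. If lost women do worse than those observed by 0.25 or 0.5 SD, the bias is −0.03 or −0.07 SD in the first case and −0.05 or −0.10 SD in the second.

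**7. What the reported drop-out shows.** The denominator is not given. If it were 4 of 5 or 4 of 6 (assumed), exact 95% limits are 28–99% and 22–96%. Both lower limits exceed 20%, but they are not clearly above the 27% used for TXA in step 3.

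**The case against.** The strongest case on the other side has four parts.

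- **At the planned attrition the effect is small.** With a common gap, bias is at most 0.07 SD over the range shown, and observed-case power stays at the 90% target. This stands. Larger figures need heavier loss or gaps chosen to differ by arm, and some unequal pairs give almost no bias.
- **The evidence of heavy loss is thin.** Four women without a denominator give no rate, and the text does not separate stopping treatment from leaving the study or withdrawing consent. A reader might infer from this report, or from the 78% stopping in the claims data, that most TXA month-6 scores will be missing. The documents do not support that: stopping treatment is not loss of MMAS, and women who stop but stay in the study keep their month-6 assessment.
- **The protocol already schedules an exit score.** Footnote 6 does so. This narrows the gap without closing it, because an exit score is not a month-6 score and sections 4.4.1 and 4.4.2 do not list the MMAS.
- **A different model gains little if few women are retrieved.** This also stands. In a simulation of multiple imputation with nobody retrieved, a common gap of 0.5 SD and 78% vs 38% lost, bias fell from 0.20 to 0.05 SD, but the standard error was 0.24–0.28, so total error was about the same as under LVCF. With half retrieved, and those women better than the rest by 0.5 SD, bias was −0.09 to −0.10 SD, more than LVCF's 0.05 to 0.06.

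None of this supplies a month-6 score for withdrawn women or a primary method fixed in advance.

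**Conclusion.** The concern holds, as something that should be fixed. The documents establish three things: no month-6 MMAS is scheduled after withdrawal from the study, LVCF is the only method named and is not fixed as primary, and TXA drop-out above expectation has been reported. The conclusion that the month-6 MMAS comparison is open to bias follows from these.

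The size does not follow from the documents. The 0.03 to 0.07 SD illustration rests on an assumed split of attrition, assumed gaps and, for type I error, assumed correlations. A reader might infer that LVCF will favour LNG-IUS, or that the primary result will be invalid. Neither is supported: the sign depends on unknown gaps in both arms, and the planned attrition with a common gap gives a small effect. The point concerns the MMAS endpoint. For duration of use, the other primary endpoint, intentional discontinuation is an event and not a missing value.

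**What to change.** 1. **Section 4.4 (most of the gain).** State that stopping or switching study treatment does not by itself end data collection. Ask withdrawn women for the already scheduled 3-, 6- and 9-month MMAS unless consent is withdrawn. Make sections 4.4.1 and 4.4.2 and footnote 6 of Table 1 agree on this.
2. **Section 7.2.** Fix in advance one primary analysis that uses all observed MMAS scores, including those after stopping. One example is a likelihood-based repeated-measures model with baseline MMAS, arm, visit, arm-by-visit and the randomisation factors. Move LVCF to a sensitivity analysis and say whether a baseline score may be carried. Add a sensitivity analysis with separate shifts by arm, because retrieved women may not represent those not retrieved.

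The cost is a short amendment, revised analysis wording and a few more questionnaires, with no new visits. Confidence intervals will be wider than LVCF would show. In simulations with 78% vs 38% stopping, the standard error was 5–6% larger with 80% of stoppers' scores retrieved and 23–25% larger with 50%; power at 0.58 SD was 94–98% and 82–90%. Those simulations used multiple imputation, not the repeated-measures model, so they are only a guide. Women who withdraw consent are still not retrieved.

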5.3 Method for Assigning Subjects to Treatment Groups

After review of enrollment criteria, eligible participants will be randomly assigned to either LNG-IUS or TXA treatment. Using a computer generated random numbers sequence; our statistician will prepare the randomization code. Randomization will be stratified by BMI (≥ 30 or < 30), dysmenorrhea (yes/no) and duration of HMB (< 1 or ≥ 1 year) and will be conducted using a dynamic allocation approach based on the Pocock-Simon method.

For patients that decline randomization but meet criteria and are interested in participation, they will be followed in the treatment group that they choose (either the LNG-IUS or TXA options).

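### No primary model is named for 6-month MMAS, and neither model listed adjusts for the minimisation factors, so precision that costs almost nothing goes unused

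*Combined protocol and SAP*

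**What the plan says.** For the continuous outcomes, which include MMAS total score, section 7.2 states that at 3, 6 and 9 months "each of the continuously scaled outcomes will be compared between treatment arms based on fitting separate linear regression models". No covariates are listed for these models. It then adds a second set: "In addition, separate analysis of covariance (ANOCOVA) models will be fit to compare the measures between the two treatment arms after adjusting". The only covariate named there is the outcome's baseline value. The Study Summary repeats both. Neither place says which one decides the 6-month MMAS comparison, and 7.2 sets the same two-sided 0.05 threshold for every test.

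Section 5.3 stratifies allocation by BMI, dysmenorrhea and duration of HMB, and the allocation "will be conducted using a dynamic allocation approach based on the Pocock-Simon method". No section puts these factors into an MMAS model.

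On endpoints, section 3.2 has two: "The primary endpoints are the difference in self-reported MMAS scores at 6 months between LNG-IUS and TXA treatment and the duration of use". Section 7.1 has one: "The primary outcome variable will be the difference in MMAS score at 6 months between the treatment arms". Section 7.1 also gives power for continued use at 6 months. The primary hypothesis, in sections 2 and 7.2, is that LNG-IUS "will result in better patient reported outcomes and longer use compared to self-administered medication". No section says whether one or both endpoints must succeed.

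**The concern.** Three things are left open or unused.

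- **Deciding model.** In an open-label trial with two models and no stated primary, the model reported as decisive could be settled after the results are known.
- **Precision.** A baseline-adjusted model is normally more precise than an unadjusted one. Minimisation also removes between-arm imbalance in the three factors. A model that ignores them still counts their variation as noise, so its standard error is too large whenever the factors are prognostic.
- **Success rule.** With two primary endpoints in one section and one in another, a reader cannot tell what result would support the primary hypothesis.

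At stake are the clarity of the main claim and some power. The validity of the design is not in question.

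**Working it through.** **Inputs from section 7.1:** effect 0.58 SD; two-sided 0.05; two-sample t-test; 64 evaluable and 80 enrolled per arm; 20% loss; continued use 62% vs 22%.

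**Assumed, because the documents give no values:** correlation r between baseline and 6-month MMAS of 0.3-0.6; share of outcome variance explained by the factors of 0, 10 or 20%; factor prevalence 50%; minimisation coin 0.8; the analysable split in step 5.

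**1. The plan's own figure.** The noncentrality is 0.58 × √(64/2) = 3.28 on 126 degrees of freedom, which gives 90.2% power. The exact requirement is 63.4 per arm, rounded up to 64, and 64/(1 − 0.20) = 80. Both figures reproduce.

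**2. Baseline ANCOVA.** The effective effect is 0.58/√(1 − r²), with one more degree of freedom used.

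| r | effective effect | power at 64 per arm |
|---|---|---|
| none (unadjusted) | 0.580 | 90.2% |
| 0.3 | 0.608 | 92.7% |
| 0.4 | 0.633 | 94.4% |
| 0.5 | 0.670 | 96.4% |
| 0.6 | 0.725 | 98.3% |

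**3. Leaving out the minimisation factors.** Pocock-Simon allocation of 128 women on three binary factors was simulated under no treatment effect, with 10,000 runs per cell. The simulation error near 5% is √(0.05 × 0.95/10,000), or about 0.2 point. Null rejection of the baseline-only ANCOVA at r = 0.3/0.4/0.5/0.6 was:

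| factors | 10% of variance | 20% of variance |
|---|---|---|
| unrelated to baseline MMAS | 3.8/3.7/3.7/3.4% | 2.4/2.7/2.6/2.1% |
| equal effect on baseline and 6-month MMAS | 4.4/4.2/4.4/4.7% | 4.0/4.1/4.1/4.4% |

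With the factors as covariates, rejection was 4.6-5.2% in all these cells. With factors at 10% of variance, adding them raised power by 0.1 point (97.9 to 98.0%) to 1.4 points (94.0 to 95.4%). If they have no effect, the three extra degrees of freedom cost about 0.1 point or less.

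These are complete-data results. When 160 women were minimised and 72 LNG-IUS and 24 TXA women were kept at random (r = 0.5, factors unrelated to baseline, 6,000 runs), baseline-only rejection was 4.8% (10% of variance) and 3.7% (20%). The comparable complete-data values were 3.9% and 2.6%.

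**4. Letting either model count.** With no factor effect, a significant result in at least one of the two models occurred in 6.4/6.65/7.3/7.9% of null trials at r = 0.3/0.4/0.5/0.6. With factors prognostic and unrelated to baseline, this was 5.0-6.2% (10% of variance) or 3.5-4.4% (20%). The inflation here and the conservatism in step 3 therefore do not occur at full size together.

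**5. Unequal drop-out.** Section 1.1 reports that nearly all randomised TXA participants (n = 4) left before 6 months. At an assumed 72/24 analysable, noncentrality is 0.58 × √(72 × 24/96) = 2.46. Power is 68.3% unadjusted and 80.3% with ANCOVA at r = 0.5. The result depends on the split: at 72/40 these become 83.0% and 92.0%, and at 72/16 the ANCOVA figure is 66.8%.

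**6. Endpoint rule.** Power for 62% vs 22% at 80 per arm is 99.97%. If both endpoints must succeed at 0.05, no alpha split is needed. Joint power is about 0.9025 × 0.9997 = 90.2%, assuming independence and using the plan's 6-month chi-square test as a stand-in for duration of use. So 64/80 per arm stands.

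**The case against.** The model choice is less open than the missing label suggests. The sample size in 7.1 rests on a two-sample t-test, which is the unadjusted regression. Section 7.2 lists that regression first and brings in ANCOVA as an addition. This stands: the natural reading is that the unadjusted model is the main one. But it is only an inference, and it points to the less precise of the two.

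Adjusting for the minimisation factors may be called a preference. The documents give no prognostic strength for them, omission is conservative, the power gain at 10% of variance is 1.4 points at most, and the conservatism shrinks under heavy unequal drop-out. All of that stands. The case for including them is a correctly sized test and some precision, from data already collected for allocation.

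Three stronger readings are tempting, and the documents do not support them:

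- **Omitting the factors inflates false positives.** The effect goes the other way (step 3).
- **The trial is underpowered as planned.** The unadjusted test meets the 90% target under the plan's own assumptions.
- **Two primary endpoints give 1 − 0.95² = 9.75% error.** That needs independent endpoints and a rule that either one suffices, which no section states. The hypothesis joins the two endpoints, and under that reading nothing inflates. Nor is duration dropped in 7.1, which gives power for continued use. The mismatch is one of labels.

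**Conclusion.** The point holds as a matter of specification and precision. Section 7.2 should say which model decides 6-month MMAS, and the model that the text seems to favour is the weaker one. Under the plan's effect size, baseline adjustment is worth about 2.5 to 8.1 points of power (92.7 − 90.2 to 98.3 − 90.2) for assumed correlations of 0.3-0.6. If the factors explain 10-20% of variance and are unrelated to baseline, omitting them lowers null rejection to about 2-4% in complete data, and including them restores about 5%. Naming one model also removes a possible 6.4-7.9% error rate, which arises only if either model could count and the factors have no effect.

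None of this corrects bias from unequal TXA drop-out. ANCOVA recovers some power in that case, but at 72/24 and r = 0.5 it does not restore 90%.

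The endpoint mismatch is secondary. It needs consistent labels and a stated rule, not a larger trial. The correlations, factor strength, prevalence, coin probability and drop-out splits are all assumptions.

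**What to change.** In section 7.2, name one primary analysis: ANCOVA of 6-month MMAS total score in all randomised women, with baseline MMAS, BMI group, dysmenorrhea and HMB duration group as covariates. Label the unadjusted regression and the 3- and 9-month tests as supportive. Carry the same wording into the Study Summary.

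In sections 3.2 and 7.1, use the same primary-endpoint labels. State that the joint hypothesis is supported only if both MMAS and duration of use succeed at two-sided 0.05.

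The cost is SAP text and three degrees of freedom. No added patients, visits or data are needed, and the sample size is unchanged. The change should be made before outcome data are analysed.

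Testing MMAS first and duration only if MMAS succeeds is optional. It would let MMAS be claimed alone, but it caps the chance of a formal duration claim at the MMAS power. That cap could fall well below 90% under unequal drop-out, for example 68-80% at the assumed 72/24 split.
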